Fundación Universitaria Autónoma de las Américas

Universidad del Quindío

Universidad Tecnológica de Pereira

Hospital San Jorge E.S.E Pereira

List of abbreviations

ALT	Alanine aminotransferase
AST	Aspartate aminotransferase
AZT/3TC	Zidovudine/lamivudine
ABC/3TC	Abacavir/lamivudine
CDC	Centers for Disease Control and Prevention.
Cels/ μ l	Cells per microliter
CRF	Case Report Form
CTCAE	CTCAE, Common Terminology Criteria for Adverse Events
DAIDS	DAIDS Adverse Event Grading Tables
BD	Bone density
AE	Adverse Event
EFV	Efavirenz
ELISA	Enzyme-linked immunosorbent assay
PPE	Personal protective equipment
FDA	Food and Drug Administration
Hb	Hemoglobin
MSM	Men sex with men
HUSI	Hospital Universitario San Ignacio
INR	International standardized ratio

IPS	Health care provider institution
IRB	Institutional review board
ULN	Upper normal limit (with regards to lab testing)
mg/dl	Milligrams per deciliter
WHO	World Health Organization
PTT	Partial Thromboplastin Time
PUJ	Pontificia Universidad Javeriana
PrEP	Pre-exposure prophylaxis
RT-PCR	Real time polymerase chain reaction.
SARS-CoV-2	Severe acute respiratory syndrome coronavirus 2
SOP`s	Standard Operating Procedures
TDF/FTC	Tenofovir Disoproxil fumarate and Emtricitabine
TLR	Toll-like receptor
UAA	Universidad Autónoma de las Américas
ICU	Intensive Care Unit
UQ	Universidad del Quindío
UTP	Universidad Tecnológica de Pereira
HIV	Human Immunodeficiency virus
HBV	Hepatitis B virus

Summary of the study

Title	Effectiveness of the use of Tenofovir/Emtricitabine in addition to personal protective equipment for the prevention of the transmission of SARS-COV-2 to health care personnel. A Randomized Clinical Trial.
Study population	Health care professionals (Physicians, Nurses, Respiratory therapists, or nursing assistants) between older than 18 years and less than 70 years, who provide health care to confirmed or suspected cases of COVID-19 in the emergency room, COVID wards, or the intensive care units from seven hospitals in Colombia.
Study design	Randomized triple-blinded multicentric clinical trial to evaluate the effectiveness and safety of Tenofovir/Emtricitabine in addition to personal protective equipment for the prevention of infection with SARS-CoV-2 in health care personnel in Colombia.
General Objective	To evaluate the effectiveness and safety of Tenofovir/Emtricitabine in addition to the use of Personal Protective Equipment (PPE) for the prevention of SARS-CoV-2 infection in health care personnel who provide health care to confirmed or suspected cases of COVID-19 in the emergency room, COVID wards and ICU.

Specific Objectives
	
 - To determine the effectiveness of Tenofovir Emtricitabine in addition to the use of Personal Protective Equipment (PPE) for the prevention of SARS-CoV-2 infection in health care personnel caring for patients with confirmed or suspected COVID-19 in the emergency room, general ward and ICU. - To evaluate the safety (adverse events frequency) of Tenofovir Emtricitabine in addition to the use of Personal Protective Equipment (PPE) for the prevention of SARS-CoV-2 infection in health care personnel caring for patients with confirmed or suspected COVID-19 in the emergency room, general ward and ICU. - To evaluate the adherence to Tenofovir Emtricitabine of health care personnel caring for patients with confirmed or suspected COVID-19 in the emergency room, general ward, and ICU. - To determine the frequency of discontinuation for any reason of Tenofovir Emtricitabine in health care personnel caring for patients with confirmed or suspected COVID-19 in the emergency room, general ward, and ICU. - To describe and compare the clinical course and severity of participants who develop COVID-19 in the intervention and control groups.

Primary Outcome
	
Incidence of SARS–CoV-2 infection in health care personnel caring for patients with confirmed or suspected COVID-19

Sample size
	
950 healthcare workers randomized 1 to 1 to the intervention group (Tenofovir Emtricitabine + PPE), or the control group (Placebo + PPE). 475 in each group

1. Background and Problem Formulation

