The hazard ratio will be estimated by comparing the risk of infection in the intervention group (TDF/FTC + EPP), with the risk in the control group (placebo + EPP), with a confidence interval of 95 %, using a univariate Cox regression model.

If necessary, adjustment will be made for variables that may affect the occurrence of the primary outcome and that are not balanced between the intervention group and the placebo group; The need for adjustment with an OR greater than 1.5 will be considered for dichotomous categorical

variables, such as sex; or if there are differences between the groups greater than 0.25 of the standard deviation for continuous variables such as age, adherence to pharmacological intervention or EPP, and hours of exposure to the COVID area. For the calculation of the adjusted hazard ratio, a multivariate Cox proportional hazards model will be used, if the proportionality assumption is met, or an extended Cox model if this assumption is not met.

For secondary outcomes

-The proportion of incidence of total adverse effects in each group will be determined at day 60 after randomization, estimated as the cumulative incidence using the Kaplan Meier method.

The hazard ratio ("Hazard Ratio") will be estimated by comparing the risk of adverse events in the intervention group (TDF/FTC + EPP), with the risk in the control group (placebo + EPP), with a confidence interval of 95%, using a univariate Cox regression model.

Additionally, the same analysis will be performed for serious adverse events.

- The proportion of incidence of discontinuation of the intervention in each group, for any reason, will be determined at day 60 after randomization, estimated as the cumulative incidence using the Kaplan Meier method.

The hazard ratio will be estimated by comparing the discontinuation of the intervention in the intervention group (TDF/FTC + EPP), with the risk in the control group (placebo + EPP), with a confidence interval of 95 %, using a univariate Cox regression model.

- It will be determined as the difference in the mean or median (according to the distribution of the data) of the percentage in which the individuals were adherent

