6.1. Definitions

- Adverse event (AE)

Any adverse medical occurrence in a patient or subject of a clinical investigation to whom a pharmaceutical product was administered and that does not necessarily have a causal relationship with this treatment. Therefore, an adverse event (AE) can be any unfavorable and unintended sign (including an abnormal laboratory finding), symptom or illness temporarily associated with the use of a medicinal (research) product, whether it is related. (104).

Considering the above, the United States National Institute of Health in conjunction with the National Cancer Institute of the same country published standardized definitions of adverse events known as Common Terminology Criteria for Adverse Events (CTCAE). Events, for its acronym in English), to describe the severity of the organic damage caused to patients by the various medications (104,105). According to them, the following events are considered:

- Serious adverse event (SAE)

Any unfavorable occurrence than at any dose that:

- Results in death.
- Is life threatening, requires hospitalization of the patient or prolongation of existing hospitalization.
- Results in persistent or significant disability / disability.
- Generates a congenital anomaly / birth defect.

- Fatal Serious Adverse Event.

EAS that end in the death of the subject or threaten the life of the same.

- Expected / Listed Serious Adverse Event.

EAS whose specificity or severity is consistent with that described in the Research Protocol, Investigator's Manual / basic prescription information or product label.

- Unexpected / Unlisted Serious Adverse Event.

EAS whose specificity or severity is not consistent with that described in the Research Protocol, Investigator's Manual / basic prescription information or product label.

- Non-Serious adverse event

All other events that do not meet any of the EAS seriousness criteria

- Adverse event requested

They are the AE that will be searched for in each assessment of the subjects participating in the study.

- Unsolicited adverse events

They are the AEs that are voluntarily manifested by the patient that may or may not be related to the study drug.

6.2. Assessment and documentation of adverse events.

The researcher assigned to follow up the study subjects will be responsible for recording all adverse events in each participating institution, regardless of the group evaluated, with the following exceptions:

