Laboratory abnormality	Mild (Grade 1) **	Moderate (Grade 2)	Severe (Grade 3)	Potentially Life Threatening (Grade 4)	Death (Grade 5)
Laboratory					
ALT and AST	>3 x ULN if baseline was normal. 1.5-3 x ULN of baseline if it was not normal.	>3-5 x ULN if baseline was normal. >3-5 x ULN of baseline if it was not normal.	>5-20 x ULN if baseline was normal. >5-20 x ULN of baseline if it was not normal.	>20 x LSN ULN if baseline was normal. >20 x ULN of baseline if it was not normal.	
Hemoconcentration	Rise of 0-2 g/dl from baseline.	Rise of 2-4 g/dl from baseline.	Rise of > 4 g/dl from baseline.		
Anemia	Hb<ULN-10g/dl	Hb<10-8g/dl	Hb<8g/dl	Life Threatening; Medical	Death

				intervention is required.	
Lymphocytes Decrease - cell/mm³	< 800/mm ³ ; < ULN - 0.8 x 10e9/L	<800 - 500/mm ³ ; <0.8 - 0.5 x 10e9 /L	<500 - 200/mm ³ ; <0.5 - 0.2 x 10e9 /L	<200/mm ³ ; <0.2 x 10e9 /L	
Neutrophils Decrease - cell/mm³	<LLN - 1500/mm ³ ; <LIN - 1.5 x 10e9 /L	<1500 - 1000/mm ³ ; <1.5 - 1.0 x 10e9 /L	<1000 - 500/mm ³ ; <1.0 - 0.5 x 10e9 /L	<500/mm ³ ; <0.5 x 10e9 /L	
Platelets Decreased - cell/mm³	<LLN - 75,000/mm ³ ; <LLN - 75.0 x 10e9 /L	<75,000 - 50,000/mm ³ ; <75.0 - 50.0 x 10e9 /L	<50,000 - 25,000/mm ³ ; <50.0 - 25.0 x 10e9 /L	<25,000/mm ³ ; <25.0 x 10e9	
Creatinine – mg/dL	Rise of 1.5x ULN	Rise of 1.5 – 3x from baseline; 1.5 – 3 x ULN	Rise of 3x ULN from baseline.; 3 – 6 x ULN	Rise of 6x ULN	

ULN: Upper limit of normal range. LLN: Lower limit of the normal range.

Table 5. Causation of adverse events. Taken from the Common Terminology Criteria for Adverse Events (104,105).

Imputed causation	Definition
Definitive	A clinical event, or alterations in laboratory tests, that manifests with a plausible temporal sequence in relation to the administration of the drug, and that cannot be explained by the concurrent disease, or by other drugs or substances. The response to drug withdrawal (withdrawal; dechallenge) must be clinically plausible. The event must be definitive from a pharmacological or phenomenological point of view, with a conclusive re-exposure (rechallenge).
Probable	A clinical event, or alterations in laboratory tests, that manifests with a reasonable time sequence in relation to the administration of the drug, that is unlikely to be attributed to the concurrent disease, or to other drugs or substances, and that when withdrawing the drug presents a clinically reasonable response. Information on re-exposure is not required to assign this definition.

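### The laboratory grading table starts Grade 1 for low hemoglobin, and in part for low lymphocytes, at the upper limit of normal, so in-range blood counts would be coded as mild abnormalities.

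*Combined protocol and SAP*

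**What the plan says.** The abbreviation list expands ULN as "Upper normal limit (with regards to lab testing". The footnote of the laboratory table in section 6.3 (the first of two tables numbered 5) repeats this and adds the lower limit: "ULN: Upper limit of normal range. LLN: Lower limit of the normal range".

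The Grade 1 cells of that table read as follows:

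- Platelets: "<LLN - 75.0 x 10e9 /L". The neutrophil row is also anchored on LLN.
- Anemia: hemoglobin below ULN, down to 10 g/dl.
- Lymphocytes: two cut-offs in one cell, below 800/mm³ and "< ULN - 0.8 x 10e9/L". Grade 2 is 800 down to 500/mm³.
- ALT/AST: ">3 x ULN if baseline was normal". Grade 2 with a normal baseline is above 3 and up to 5 times ULN.
- Hemoconcentration: "Rise of 0-2 g/dl from baseline".

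Appendix 3 collects an anemia grade and a lymphopenia grade at follow-up 3, each coded 0 for normal and 1 to 4 for the grades. It also collects the hemoglobin concentration and the lymphocyte count.

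On what counts as an event, section 6.1 defines an adverse event as an unfavorable, unintended sign, "including an abnormal laboratory finding". Section 6.3 assigns a grade only after that definition is met. Section 3.6.8 has results read against the laboratory's own normal values together with the protocol's grading criteria. Section 4 plans this analysis: "The proportion of incidence of total adverse effects in each group will be determined at day 60 after randomization", by Kaplan-Meier with a univariate Cox hazard ratio. It also plans the same analysis for serious events.

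**The concern.** A grade for a low value cannot begin at the upper limit of normal. As printed, any hemoglobin from 10 g/dl up to the upper limit is Grade 1 anemia, and the normal code in Appendix 3 is left for people at or above that limit. The same follows for lymphocytes if the half of the cell in 10e9/L is used.

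The other Grade 1 cells add to the problem. An ALT of 4 times ULN after a normal baseline satisfies both Grade 1 and Grade 2, while a rise to 3 times ULN or less has no grade. Any small upward fluctuation in hemoglobin is graded as hemoconcentration.

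Two things are at stake. The first is the meaning of the graded laboratory variables, which several sites and laboratories could resolve in different ways. The second, conditionally, is the comparison of total adverse events, because an abnormal laboratory finding is an adverse event and section 4 does not say whether graded laboratory values enter. Safety is part of the general objective, and section 4.1 states that there is no data monitoring committee, so the grading rules carry more weight than usual.

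**Working it through.** The plan states no figure for the share of participants graded, so there is nothing of its own to reproduce.

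**Inputs.** From the documents: 475 participants per arm (section 3.4), baseline hemoglobin below 11 g/dl excluded (section 3.2), and the Table 5 cells. Assumed, because the documents do not give it: each laboratory's reference interval covers a central share c of healthy people, with c = 0.95 and a range of 0.90 to 0.99.

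**Step 1: share coded Grade 1 anemia.** The share below ULN is (1 + c)/2, and the share below LLN is (1 − c)/2.

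| c | Below ULN (as printed) | Below LLN |
|---|---|---|
| 0.90 | 0.950 × 475 = 451 | 0.050 × 475 = 24 |
| 0.95 | 0.975 × 475 = 463 | 0.025 × 475 = 12 |
| 0.99 | 0.995 × 475 = 473 | 0.005 × 475 = 2 |

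The 11 g/dl exclusion barely matters. Normal models truncated at 11 g/dl, with assumed ranges of 12–16, 13.5–17.5, 12–15.5 and 13–18 g/dl, all give 97.5% with ULN and 2.3% to 2.5% with LLN.

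**Step 2: lymphocytes.** Lognormal models with assumed ranges of 1.0–4.0 and 1.2–3.5 × 10e9/L put 97.0% and 97.5% in the half of the cell that uses ULN. They put only 0.5% and 0.03% below 800/mm³. The two halves of one cell therefore grade almost everyone or almost no one.

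**Step 3: the total adverse-event comparison, only if every printed Grade 1 value counts as an event at day 60.** Let p be the control risk of other adverse events by day 60, and take a true hazard ratio of 1.5. Both are assumptions. With 97.5% of participants flagged in each arm, the incidence is 1 − (1 − p) × 0.025 in controls and 1 − (1 − p)^1.5 × 0.025 on active drug:

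- p = 0.20: 1 − 0.80 × 0.025 = 98.0%, and 1 − 0.716 × 0.025 = 98.2%.
- p = 0.40: 1 − 0.60 × 0.025 = 98.5%, and 1 − 0.465 × 0.025 = 98.8%.

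Cox models were simulated with 475 per arm, 300 replicates, exponential event times, and laboratory flags added at day 60 independently of arm. The ranges cover Efron and Breslow handling of ties.

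| p | Flagged | Hazard ratio | Power |
|---|---|---|---|
| 0.20 | none | 1.51–1.52 | 0.87–0.90 |
| 0.20 | 97.5% | 1.10–1.11 | 0.19–0.27 |
| 0.20 | 5% | 1.40–1.41 | 0.75–0.80 |
| 0.40 | none | 1.50–1.52 | 0.99–1.00 |
| 0.40 | 97.5% | 1.21 | 0.87–0.90 |
| 0.40 | 5% | 1.45–1.47 | 0.98–0.99 |

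The 5% rows approximate two tests with LLN in place (2 × 2.5%).

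**The case against.** The best defence is that Table 5 grades severity and does not define abnormality. Section 6.3 grades an event only once it meets the adverse-event definition, and section 3.6.8 refers to the laboratory's normal values. An in-range hemoglobin would then never become an adverse event. Appendix 3 supports this: adverse events have their own yes/no and type variables, the listed non-serious types are symptoms and reactions plus an open category, and no text feeds the laboratory grade codes into the section 4 analysis. This stands. A reader might infer from the table that the adverse-event comparison is bound to be swamped and a real excess of harm hidden. The documents do not support that, because it needs a counting rule that they do not state.

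The defence does not clear the table. The Appendix 3 anemia and lymphopenia grades are not conditioned on an adverse event having been declared, section 3.6.8 sets no precedence when laboratory normals and protocol grades disagree, and section 4 is silent.

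Other points on the same side also stand:

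- The abbreviation list is correct; the error lies in Table 5.
- The slip looks like translation, since untranslated abbreviations remain in the same table.
- It is the same in both blinded arms.
- The primary outcome, the serious-event analysis and the kidney withdrawal criterion do not use these cells.
- Raw values are collected, so grades can be derived again, although Appendix 3 lists no variable for the laboratory's limits.
- The timing of flags is uncertain: Table 1 puts the follow-up blood count at day 60, while Table 6 appears to mark it at visits 2 and 4, and visit 4 falls after the day-60 horizon.

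**Conclusion.** Table 5 is wrong as written and should be corrected. The ULN error in the anemia cell and in half of the lymphocyte cell is plain from the table's own footnote and sibling rows, and so is the conflict inside the lymphocyte cell. The ALT/AST overlap and gap, and the open-ended hemoconcentration cell, are separate defects in the same table.

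Read literally, about 97.5% of healthy participants would be coded Grade 1 anemia (463 of 475 per arm; 95% to 99.5% across the assumed intervals), against about 2.5% with the lower limit (0.5% to 5%). The figure rests on an assumed reference interval. It should not be carried over to lymphocytes without saying that the other half of that cell grades under 1% in the ranges tried.

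The effect on the treatment comparison is conditional. If every printed Grade 1 value were counted, day-60 incidence would be about 98% or more in both arms and the hazard ratio would move toward 1. The loss would depend heavily on the rate of other adverse events: power under literal counting runs from about 0.19 to 0.90 over the two rates tried. If laboratory normals are applied first, this does not happen.

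**What to change.** - In Table 5 (laboratory abnormalities), replace ULN with LLN in the Grade 1 cells for anemia and lymphocytes, to match the neutrophil and platelet rows, and remove the stand-alone cut-off of 800/mm³ from the lymphocyte Grade 1 cell.
- Reconcile the ALT/AST and hemoconcentration Grade 1 cells with their neighbouring grades and with the laboratory normal values that section 3.6.8 relies on, so that grades do not overlap and in-range values are not graded. The choice of limits is for the sponsor.
- Align the Appendix 3 grade codes with the corrected table, and add LLN to the abbreviation list.
- State in section 4 that only values outside the laboratory's normal range can enter the analysis of total adverse events.

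The cost is the wording of a few cells, one sentence in section 4 and the eCRF grade checks. No new data, visits or participants are needed.

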1.1. Approach and justification

The global impact of SARS-CoV-2/COVID-19 is unprecedented, and it is the greatest pandemic of a respiratory virus since the 1918 Influenza. With high infectiousness, important morbidity and relatively high fatality in specific groups of the population, an attack rate of approximately 80%(1), and no vaccine available yet, the pandemic will exceed the capacity of the health care systems in many settings. The health care personnel represent the most valuable resource to respond to the challenges imposed by this pandemic. As health care professionals are in the frontline of response and at a high risk of infection, it is extremely important to establish effective prevention strategies that protect them from becoming infected (2).

The main mode of transmission for SARS-CoV-2 infection is person to person through direct contact, droplets, or fomites. Moreover, aerosol-generating procedures have also been documented to transmit the infection (3,4). In countries such as Italy, where the pandemic had an accelerated behavior and high mortality rates, it has been estimated than from the total of infected people 7-9% corresponds to health care workers (5). Additionally, data from China and The USA show that between 3.8 and 19 % from the total of infected people are health care personnel, respectively (5-7). First, not only do They represent the initial barrier of response in any epidemic which increments by itself the exposition to the pathogen but by having asymptomatic infected individuals use of proper personal protective equipment may be missed.

Both hand hygiene and the use of Personal Protective Equipment (PPE) such as surgical gown, gloves, ocular protection, surgical mask, or N-95 respirator, are considered key strategies for the prevention of infection in health care professionals (8). However, there are few studies estimating the probability of infection with their use. Moreover, several pharmacological agents have been considered for a prophylactic use in SARS-CoV-2 infection.

As of today, there is preclinical evidence, principally in vitro, indicating antiviral effect of Tenofovir Disoproxil Fumarate / Emtiricitabine (TDF/FTC) on the SARS-CoV-2 RNA depended RNA polymerase (9). TDF/FTC is an approved drug for HIV treatment in combination with other antiretroviral drugs. It is widely used as HIV pre and post exposure prophylaxis, and it is the election therapy for Hepatitis B infection (10-13).

Knowing that TDF/FTC is a drug with a known security profile, has low frequency of short-term adverse events, and is capable of inhibiting SARS-CoV-2 replication in vitro, it is an interesting alternative to evaluate as prophylaxis for SARS-CoV-2 infection. On the other hand, in Spaniard HIV programs it has been noticed that in HIV positive patients under antiretroviral therapy, even those older than 50 years, a lower burden of covid-19 is observed compared to general population (14), despite of chronic inflammation and rapid immunosenescence, which is characteristic in this type of population (15). Furthermore, recently, in a clinical cohort of 77590 persons living with HIV, it was documented that those receiving TDF/FTC had a risk of COVID 19 and related hospitalization between 37 a 57% lower than those who were taking other antiretroviral medications.

Nevertheless, this observation must be evaluated rigorously, considering that it might be possible this population, knowing their risk, could have been more adherent to preventions measurements.

Consequently, we consider relevant and justified to evaluate the use of TDF/FTC for the prevention of SARS-CoV-2 infection in a high-risk population, such as health care professionals providing clinical care to confirmed or suspected cases of COVID-19 through a clinical trial. Thus, allowing to establish prevention strategies with higher scientific evidence.

